**Sample size and power.** Power analyses are performed for primary hypotheses *1a, 1b and 2a*, incorporating the longitudinal nature of the design. We propose a Random Regression model (also known as Multilevel or Growth Curve Models) as a basis of the analysis. In this approach, the repeated measures over time for each individual subject form a trajectory that can be described by a relatively simple model with a few parameters, here a linear model described by intercept (baseline value) and slope (rate of change). With random assignment to groups, there should be no group differences in baseline values, and slopes differences reflect treatment effects. With repeated measures, repeated observations within subjects are potentially correlated, impacting tests of significance. When within subject correlation is properly incorporated, the repeated measures analysis takes full advantage of all information obtained from each subject, thereby greatly increasing statistical power over cross-sectional methods. This approach can model differential patterns over repeated assessments instead of totals at one point and therefore increases the reliability of the measurement of response (since the slope combines repeated measures which cancel much of the error of measurement), and increases the protection against the major effects of missing data (since one can impute from the non-missing data for that subject as well as for other similar subjects). These result in increased power to detect effects and precision of effect size estimation without increased sample size.

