Power calculations can be made for repeated measures designs under specified assumptions. Hedeker et al. extend Diggle et al.'s method for various covariance structures. Procedures described by Hedeker et al. for Random Regression Models were used for the proposed study to estimate needed sample size using RMASS (see Hedeker <http://tigger.uic.edu/~hedeker/ml.html>). Data from our previous studies were used to calculate effect sizes. The design consists of a 2 (sites) X 2 (CABA vs TAU) X 4 (baseline, 7, and 14 weeks) where the slope is the dependent measure. Site and Treatment by Site interaction were included as "nuisance parameters", that is, included to account for possible overall site effects (Site) or possible site differences in treatment effects (Treatments X Site). With a balanced design (equal numbers at each site in each group), ignoring these would not increase the probability of Type I error, but would increase the Error Sum of Squares (SS) and probability of Type II error. The main effect of treatment represents the common effect size across sites if there is one, or the average site effect, if there is heterogeneity across sites. This is true because sample sizes will be balanced across treatment groups and sites. In any case, the analysis procedures will include site and site interaction effects to avoid allowing site effects to bias treatment comparisons. However, if we detect imbalances between the treatment groups within each site, we will follow the primary analyses with subsequent analyses considering the imbalances to verify that conclusions are not affected by imbalances.

Other assumptions needed are number of repeated measures, alpha-level, nature of the hypothesis (one- or two-sided), drop-out rate, and variance-covariance matrix of the longitudinal data. We assume an overall Type-I error levels alpha of .01 to .02, drop-out rate of 15%, and autoregressive covariance structure, with correlation between sequential assessments set at 0.45. Autoregressive covariance structures assume points closer together in time are more correlated than points further in time, which is more plausible compared to the equal correlation between all pair of assessments regardless of time separation assumed by the compound symmetry design. *When multiple analyses are conducted for a given hypothesis, Type I error rates will be controlled*

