*by a Westfall-Young procedure, we would include an alpha level of .04 for Hypothesis 1a, .03 for Hypothesis 1b and 2a, and .05 for Hypothesis 2b.* We estimate that with the proposed sample size of 192 (15% drop-out) patients (96 for each of the two groups), the study will have minimum power of 80% to yield a statistically significant result for a medium effect size. Hedker et al. defined medium effect size in this model as a between-group difference increasing linearly from 0 at baseline to .5 SD units at the last time point. Hypothesis 2b is a cross-sectional hypothesis using data collected only in the week 14 of the study. The proposed sample size will provided us with a minimum power of 90% to detect a medium to large effect size. The former and foundational Behavioral Activation for PTSD study by [name] and [name] yielded the following rates which also informed our proposed sample size determination: 192 screened, 81 enrolled, 10 dropped (12.3% dropout rate), 101 screen failures.

**Outcome analyses:** Data analyses will proceed in stages. Descriptive statistics and exploratory graphing such as frequencies, means, standard deviations, stem and leaf diagrams, and scatterplots will be used to assess normality of data in terms of presence of skew and/or outliers. Continuous outcome data will be transformed if necessary using an appropriate transformation such as the log transform for skewed long tailed data. Prior experience with this kind of data leads us to expect that for all variables, the distributions will be skewed and the variances not homogeneous. Similarly, potential covariates will be summarized with descriptive statistics and graphs to determine the most appropriate way to treat these variables (e.g., continuous, categorical, or interval representation). For outcome measures acquired at baseline, 7, and 14 weeks, the analytical approach will address the nature of the outcome, as well as accommodate the within

individual variability due to the repeated assessments. Results from will be inspected for bias due to drop-outs or missing data.

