For major analyses of central hypotheses (1a-1b and 2a), we propose to use Mixed Effects modeling to account for clustered data (i.e., repeated assessments within individuals, treatment groups, and sites). The mixed effects approach provides more information and more power compared to cross-sectional analyses which focus on analysis of one summary index or time-until event methods and traditional analytic approaches such as a change score, end-point or repeated measures analysis of variance (ANOVA). This method allows inclusion of subjects with missing data or those who were terminated early in the study, without relying on data imputation procedures. Two specific forms of the Mixed effects model strategy are commonly implemented: random regression models, or hierarchical models (HLM) or multilevel models; and mixed model analysis of variance (MMANOVA). Each outcome variable will be graphed versus time for each subject to evaluate what function of time best describes the data. The mixed effects framework is robust with respect to drop-out and missing data, unless the drop-out mechanism or cause of missing is informative. We will use pattern-mixture models to assess if there is bias due to drop out or missing data. As described by Hedeker and Gibbons, these mixed models allow us to assess whether important estimates are dependent on missing data patterns and provide overall estimates of effects by averaging over the various missing-data patterns. In addition, we will consider the extension of the Pattern-Mixture models as described by Guo et al which includes the incorporation of random effects in the Pattern mixture model, allowing subject-to-subject heterogeneity.

Missing data values will be minimized by intensive training of interviewers in techniques of clarifying answers and checking questionnaires while participants are on-site. When missing values are identified, we will employ several approaches. If possible, participants will be rescheduled for missed assessments. Missing data will be examined to assess randomness. The pattern of missing data will be examined according to the procedure recommended by Little and Rubin which includes comparing group differences in the primary outcomes of subjects with versus without missing data. The Mixed effects model allows inclusion of subjects with missing data or those who terminated the study early, without relying on data imputation procedures.

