**Hypothesis 1a)** PTSD symptom severity. Dependent variables: CAPS-V and PCL-5.

**Hypothesis 1b)** Functional impairment. Dependent variables: HVLTR, WAIS-IV (Digit Span subtest), DKEFS (Trails subtest), and COWAT (Verbal Fluency).

Independent variables: Treatment group (2 levels, CABA and TAU), & Time (3 levels, Weeks 0, 7, and 14). Statistical Analysis: We will analyze data on all randomized subjects in whom we have a baseline assessment and at least one post-baseline evaluation by Mixed effects model methods. Preliminary inspection of data will determine whether the outcome is nearly normal, or whether an appropriate transformation is required, or whether a generalized linear mixed model should be considered. The mixed effects model method provides an estimate of the individual variability around the population trend, the variability of the individual intercepts (baseline values) and slopes (changes across time), and the correlation between them. A fully saturated treatment by time model will be utilized for inference. Covariance structure will be chosen based on Akaike's Information Criterion (AIC). Random group level treatment effects will also be evaluated for importance based on the model AIC. This allows for any group level effects to be incorporated into the model. Denominator degrees of freedom will be calculated using the Kenward-Roger small sample correction. The design is a 2 (sites) X 2 (CABA vs TAU) X 3 (baseline, 7, and 14 weeks). The interaction of Site and Treatment X Site will be included and tested as

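### CAPS-V has no week-7 value and no joint model or imputation is planned, so week-7 scores of people who miss week 14 go unused; loss that differs by arm could bias the CAPS-V effect

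*Combined protocol and SAP*

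**What the plan says.** Section 5.6, under Hypothesis 1a, names two outcomes: "Dependent variables: CAPS-V and PCL-5". The model terms are treatment, time at three levels (weeks 0, 7 and 14) and site. No joint model of the two outcomes is named, and no week-7 score enters as an auxiliary variable for another outcome.

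Table 3 (section 5.5) gives CAPS-V and the neuropsychological battery at weeks 0 and 14. PCL-5, NSI, BDI-II and SLS are given at weeks 0, 7 and 14. CAPS-V therefore has two time levels, not three.

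On missing data, Sample size and power credits the method with protection "since one can impute from the non-missing data for that subject as well as for other similar subjects". Outcome analyses says twice that imputation is not needed, the second time as: "The Mixed effects model allows inclusion of subjects with missing data or those who terminated the study early, without relying on data imputation procedures". It adds pattern-mixture models and a comparison of people with and without missing data. The analysis set is everyone with a baseline and at least one post-baseline evaluation.

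**The concern.** The claimed protection comes from a person's other post-baseline visits. For CAPS-V there are none. A person with weeks 0 and 7 but not week 14 contributes at most a baseline value to the CAPS-V model. That person's week-7 PCL-5, the other Hypothesis 1a measure of PTSD severity, is in the database but unused for CAPS-V.

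This matters if leaving depends on how someone is doing at week 7 and does so differently by arm. The protocol gives reasons to think it might:
- Participants and therapists are not blinded (section 5.1, Blinding).
- CABA participants agree to refrain from additional mental health treatment for the active phase (section 5.4).
- Decline can prompt a recommendation to end participation at assessment visits in both arms, but also at treatment visits in CABA (section 5.7).

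If people who are not improving leave CABA more readily, the CAPS-V effect is overstated. If they leave TAU more readily, it is understated.

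**Working it through.** **The plan's own figure.** The target is "a between-group difference increasing linearly from 0 at baseline to .5 SD units at the last time point". The inputs include: "We assume an overall Type-I error levels alpha of .01 to .02, drop-out rate of 15%, and autoregressive covariance structure". A two-sided week-14 comparison at alpha .02 with 80% power needs 2 × (2.326 + 0.842)² / 0.5² = 80.3, so 81 per arm. Then 81 / 0.85 = 95.3, so 96 per arm and 192 in all, as stated. The calculation allows for 15% loss, or 0.15 × 96 = 14.4 people per arm.

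**Bias when CAPS-V is modelled alone.** All scores are in SD units. Let loss at week 14 depend on week-7 PCL-5, and let m be the shift in mean week-7 PCL-5 among those who stay. For a likelihood model of CAPS-V at weeks 0 and 14, the bias in one arm's week-14 mean is approximately

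bias ≈ g × m, with g = r(CAPS14, PCL7) − r(CAPS0, CAPS14) × r(CAPS0, PCL7).

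The bias in the treatment effect is the difference between arms. If g × m is the same in both arms, it cancels.

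**Inputs.** From the plan: correlation 0.45 between sequential assessments, autoregressive, so 0.45² = 0.2025 between weeks 0 and 14. Assumptions, not in the documents: same-visit CAPS/PCL correlation 0.8; log-odds of loss of 1 to 2 per SD of week-7 PCL-5; and a second, stronger correlation set (weeks 0–7 0.45, weeks 7–14 0.70, weeks 0–14 0.40).

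- Plan's correlations: g = 0.8 × 0.45 − 0.2025 × (0.8 × 0.45) = 0.360 − 0.073 = 0.287.
- Stronger set: g = 0.8 × 0.70 − 0.40 × (0.8 × 0.45) = 0.560 − 0.144 = 0.416.
- Size of m, by integrating the logistic loss model over a standard normal score: 0.133 (log-odds 1) and 0.203 (log-odds 2) at 15% loss; 0.091 and 0.143 at 10%; 0.173 and 0.262 at 20%.

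**Results** (absolute bias in the CAPS-V effect, SD)

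| Loss after week 7 | Smallest | Largest |
|---|---|---|
| Same rule and rate in both arms | 0 | 0 |
| 20% v 10%, same direction | 0.287 × (0.173 − 0.091) = 0.02 | 0.416 × (0.262 − 0.143) = 0.05 |
| Dependence in CABA only, 15% | 0.287 × 0.133 = 0.04 | 0.416 × 0.203 = 0.08 |
| Opposite directions, 15% each | 2 × 0.287 × 0.133 = 0.08 | 2 × 0.416 × 0.203 = 0.17 |

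Simulation with 1,000,000 per arm agrees: 0.04 to 0.09 for CABA only and 0.08 to 0.17 for opposite directions. A rerun at 15.5% loss reached 0.18 for opposite directions. A wider gap in loss, 25% v 5%, gave 0.05 to 0.10. One loss rule applied to both arms under a true 0.5 SD effect gave 0.01 to 0.02, because the treatment effect itself makes the rates differ slightly. Adding baseline and week-7 PCL-5 brought the bias to 0.00 in every scenario. PCL-5 in its own three-visit model also had 0.00 throughout.

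**At the planned size.** With 96 per arm, serial correlation 0.7, log-odds 1 and opposite directions, the bias was 0.08 SD against a standard error of about 0.16. The nominal .04 test rejected 6.9% of the time under no effect. With the directions reversed, power for 0.5 SD was 0.73, against 0.87 for the joint model.

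**Reading of the analysis set.** If people without a week-14 CAPS-V are dropped altogether, the estimate becomes the completers' change score. The bias is then 0.00 under the plan's correlations. Under the stronger set it is 0.03 to 0.05 for 25% v 5% loss, 0.03 to 0.04 for CABA only and 0.05 to 0.08 for opposite directions.

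**The case against.** A reader might infer that any drop-out predicted by week-7 status biases the primary result. The documents do not support that. A common rule and rate leaves essentially no bias, and nothing shows that loss will differ by arm. PCL-5 is also a Hypothesis 1a outcome, and its own model uses week 7.

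Other points against:
- Section 5.1 promises extensive efforts to keep in contact with people who stop treatment, section 5.7 lets those who withdraw continue paid assessments, and section 5.6 reschedules missed ones. Leaving therapy is not the same as missing week 14. This stands, and it lowers the likely size.
- Section 5.6 expects under 15% loss before the first post-baseline evaluation. If that means week 7, those people have no week-7 score to use. For CAPS-V the first such evaluation is week 14, so the sentence can be read either way.
- If part of the loss is unrelated to week-7 status, the bias shrinks further.
- Section 5.6 allows adjustment for subject characteristics and several approaches to missing values. That is permission without a commitment, and entering a post-randomisation week-7 score as an ordinary covariate would not be a proper remedy.
- The planned pattern-mixture models do not close the gap. The pattern that misses week 14 has no post-baseline CAPS-V from which to estimate its change.

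It is also tempting to extend the point at full strength to the Hypothesis 1b tests, which share the two-visit schedule. Their correlation with week-7 symptom scores is not given and may be weak, so no size can be attached to them.

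**Conclusion.** The gap is real but its effect is conditional. For CAPS-V the plan leaves collected post-baseline information unused and claims a protection that a two-visit outcome does not have. Bias arises only if loss after week 7 depends on week-7 status differently by arm, or occurs at different rates. It is then roughly 0.02 to 0.09 SD, that is 4% to 18% of the 0.5 SD target (0.02/0.5 and 0.09/0.5), and up to about 0.18 SD if the directions are opposite. These figures rest on the assumed 0.8 same-visit correlation, the two correlation sets and log-odds of 1 to 2. They assume that those lost have a week-7 score and enter the model with their baseline. The change is worth making because it is cheap and removes the bias in every scenario tried in which loss depends on week-7 PCL-5.

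**What to change.** In section 5.6 (Outcome analyses and Hypothesis 1a), do one of the following:

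- **Joint model.** Analyse CAPS-V together with PCL-5, with an unstructured covariance over CAPS-V at weeks 0 and 14 and PCL-5 at weeks 0, 7 and 14, and arm-by-time means for each. The treatment effect is the CAPS-V contrast at week 14. This needs no imputation, so the existing sentence about imputation can stay.
- **Multiple imputation by arm.** Use baseline and week-7 PCL-5, NSI, BDI-II and SLS as auxiliary variables. In that case, limit the no-imputation sentence to outcomes measured at week 7.

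State that a person with a baseline and any week-7 measure belongs in the CAPS-V analysis; otherwise the people concerned may be removed before the model is fitted. Give CAPS-V two time levels.

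For the Hypothesis 1b tests, apply the same imputation as a sensitivity analysis only.

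Cost: a slightly more complex primary model and some programming. No new data, visits or participants.

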**Cognitively Augmented Behavioral Activation for Veterans with Comorbid mTBI/PTSD**

**Protocol #: [Version 14, 8/12/2020]**

**Funding Agency: RR&D Merit Review**

**Principal Investigator/Study Chair: [name] and [name]**

## Abstract

Veterans returning from the current conflicts in Iraq and Afghanistan exhibit high rates of comorbid mTBI/PTSD. Given the comorbidity and neuropsychiatric symptom overlap of these disorders, it can be difficult to determine whether problems and disruptions in functioning are due to mTBI, PTSD, or both. Hence, it is challenging for providers to know how to prioritize these patients' clinical issues and how to effectively treat them. Currently, there are no evidence-based treatments for comorbid mTBI/PTSD. Further, it is unclear to what extent existing treatments for each disorder can be adherently and effectively implemented for the other. As such, most current treatment recommendations suggest a holistic or integrated approach to treatment for comorbid mTBI/PTSD targeting symptoms and functionality rather than underlying etiology. We are proposing a treatment for comorbid mTBI and PTSD that directly targets daily functioning and quality of life. The primary objective of this study is to evaluate the efficacy of Cognitively Augmented Behavioral Activation (CABA), a new hybrid treatment for veterans diagnosed with comorbid mild Traumatic Brain Injury (mTBI) and posttraumatic stress disorder (PTSD). The study's specific goals are to determine whether: 1) CABA reduces PTSD symptoms in veterans with mTBI/PTSD, 2) CABA reduces cognitive-related functional impairment in veterans with mTBI/PTSD, 3) CABA results in improvements in depression symptoms, cognitive functioning, and quality of life in veterans with mTBI/PTSD; and 4) CABA is an acceptable treatment for veterans with mTBI/PTSD. The overall goal is to develop an evidence-based manualized treatment for comorbid mTBI/PTSD that can be readily implemented in Veterans Health Administration (VHA) treatment settings. The study design makes use of the convergent availability of resources at the two participating Veterans Administration Medical Centers (VAMCs) in Portland, Oregon, and Seattle, Washington to conduct a Randomized Controlled Trial (RCT) of CABA. The study will recruit a total of 192 veterans  $\leq 55$  years of age, 96 participants at each site, enrolled at participating VAMCs who are diagnosed with both mTBI and PTSD. Inclusion criteria will be 1) Veterans  $\leq 55$  years of age enrolled at one of the participating VA sites who are able to provide informed consent, 2) Diagnosis of PTSD based on the Clinician Administered PTSD Scale (Blake et al., 1990), 3) Positive screen on the Structured Interview for Collecting Head Trauma Event Characteristics as outlined by the VA/DoD Clinical Practice Guideline for Management of Concussion/mTBI and positively endorsed any of the Neurobehavioral Symptom Inventory (NSI) cognitive symptoms items (items 13-17), 4) English speaking, able to attend treatment (if in CABA condition) and assessment sessions, and willing to refrain from additional mental health treatment during the first 3 1/2 months of the active phase of treatment if they are assigned to the CABA condition, and 5) Willingness to participate in audio-recorded sessions. Exclusion criteria will be 1) Current diagnosis of moderate or severe substance (alcohol) use disorder using DSM-5 criteria within the past 30 days, 2) Current Bipolar or psychotic disorder (requirement to refrain from additional treatments might be harmful), 3) Veterans with a history indicated by medical record review of a diagnosis of moderate, severe, or penetrating TBI, or self-reported history on the Structured Interview for Collecting Head Trauma Event Characteristics of TBI with PTA greater than 24 hours or LOC greater than 30 minutes, 4) Active suicidal intent indicating significant clinical risk, which would suggest that a treatment specifically targeting this intent was indicated clients who report suicidal ideation without imminent risk will be admitted into the study, 5) Initiated psychotropic medication, including Prazosin, within 4 weeks or changed dosage within 2 weeks prior to the first assessment, as this would make it difficult to determine which treatment contributed to change in the CABA condition; additionally, started or changed dosage of sleep medication or low dosages of tricyclic antidepressant or trazodone for pain or sleep within 1 week prior to the first assessment. Participants could be re-considered for eligibility after stability on medication was achieved. Enrollees will be asked, but not prohibited, to hold the doses of the current medications stable over the course of enrollment (though changes in medications after enrollment will not exclude them from on-going participation), 6) Auditory or visual impairments that would compromise ability to participate cognitive rehabilitation group or benefit from compensatory strategies. Eligible participants will be randomly assigned to either the CABA or Treatment as Usual (TAU) group. Participants in the CABA group will receive the CABA intervention via telehealth (video or telephone) during the first 14 weeks of their participation in the study, whereas TAU participants will continue to receive TAU (usual care in a PTSD specialty treatment clinic, but no CABA) during their participation in the study. Both groups will undergo evaluations at baseline, 7 weeks (mid-treatment), and 14 weeks (post-treatment). During their study participation, all participants will continue to receive their usual medical care.

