### **3.0 Objectives**

The primary objective of this study is to evaluate the efficacy of CABA for Veterans with comorbid mTBI/PTSD. The overall goal is to develop an evidence-based manualized treatment that can be readily implemented in VHA treatment settings. The study will use a randomized controlled design to address the following specific aims and hypotheses:

**Specific Aim 1:** To determine if CABA reduces PTSD symptoms.

**Specific Aim 2:** To determine if CABA reduces cognitive-related functional impairment.

**Specific Aim 3:** To determine if CABA is associated with additional positive clinical effects in patient-centered outcomes, including improved mood, adaptive cognitive function, and quality of life.

**Specific Aim 4:** To evaluate the overall acceptability of this treatment.

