#### **Primary hypotheses:**

**1a)** CABA treated comorbid mTBI/PTSD-diagnosed Veterans will demonstrate significantly decreased PTSD symptom severity compared to those receiving Treatment as Usual (TAU), defined as standard PTSD specialty care.

**1b)** CABA treated comorbid mTBI/PTSD-diagnosed Veterans will display significantly decreased cognitive-related functional impairment compared to those in the TAU group.

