#### **Secondary hypotheses:**

**2a)** CABA treated comorbid mTBI/PTSD-diagnosed Veterans will demonstrate additional significant improvements in patient-centered outcomes including depression symptom severity, cognitive symptoms, usage of cognitive strategies, and quality of life compared to a TAU group.

**2b)** Those receiving CABA will report significantly higher treatment satisfaction than those receiving TAU.

**Exploratory Investigation to Provide Guidance for Future Research Directions:** Exploratory analyses will examine possible mediator and moderator variables and secondary outcome variables, including measures of neuropsychological test performance and general functioning. We will also investigate whether CABA-associated treatment gains are maintained over a 6 month follow-up period (the 6 month follow-up is discontinued when the assessments/interventions are completed over telehealth).

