"nuisance parameters". However, we do not anticipate any Treatment by Site or Site effects with the balanced design (equal numbers at each site in each group), our standard training procedure of both sites and standard operating procedure used by both sites. In any case, the analysis procedures will include site and site interaction effects to avoid allowing site effects to bias treatment comparisons. If we detect any imbalances between the treatment groups within each site, we will follow the primary analyses above with subsequent analyses considering the imbalances to verify that the conclusions are not affected by imbalances. Analyses will be conducted within and across nested levels of the study design; this will involve within-subject analyses (comparison of occasions of measurement nested within an individual), as well as between-subject analyses (comparison of the CABA and TAU groups, comparison of groups within a site, comparison of sites, etc). Any treatment group comparison can be adjusted for subject-specific characteristics and adjustments for changes in these characteristics over the course of the study can be incorporated into single-subject analyses. All comparisons described in this section can be effectively analyzed using PROC MIXED in SAS statistical software. Based on our ongoing studies, we expect a drop-out rate of <15% after baseline assessment but prior to first post-baseline evaluation. The drop-out rate is taken into account in power analyses, see above.

**Hypothesis 2a)** Patient-centered outcomes. Dependent variables: BDI-II, NSI, and SLS. Independent variables: Treatment group (2 levels, CABA and TAU), and Time (3 levels, Weeks 0,7,14). Statistical Analysis: Data will be analyzed similar to hypotheses 1a and 1b.

**Hypothesis 2b)** Treatment satisfaction. Dependent variables: CSQ. Independent variables: Treatment group (2 levels, CABA and TAU). Statistical Analysis: Hypothesis 2b will be tested using Analysis of Variance, comparing the two groups on the treatment credibility and satisfaction (CSQ).

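### Primary hypothesis 1b is stated as cognitive-related functional impairment, but its analysis uses only cognitive tests, and no functional-impairment measure is scheduled at telehealth visits

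*Combined protocol and SAP*

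**What the plan says.** The question is stated the same way in three places. Specific goal 2 in the Abstract asks whether "CABA reduces cognitive-related functional impairment in veterans with mTBI/PTSD". Specific Aim 2 (3.0 Objectives) is "To determine if CABA reduces cognitive-related functional impairment". Primary hypothesis 1b says that CABA-treated Veterans "will display significantly decreased cognitive-related functional impairment compared to those in the TAU group".

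Section 5.6 (Data Analysis) gives the outcome set for 1b: "Functional impairment. Dependent variables: HVLTR, WAIS-IV (Digit Span subtest), DKEFS (Trails subtest), and COWAT (Verbal Fluency". Its model has treatment group and three time levels (weeks 0, 7 and 14).

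Cognitive function also appears as a separate, additional outcome. Goal 3 in the Abstract is whether "CABA results in improvements in depression symptoms, cognitive functioning, and quality of life in veterans with mTBI/PTSD", and Specific Aim 3 covers patient-centered outcomes "including improved mood, adaptive cognitive function, and quality of life". Secondary hypothesis 2a speaks of "patient-centered outcomes including depression symptom severity, cognitive symptoms, usage of cognitive strategies, and quality of life", and its analysis is "Patient-centered outcomes. Dependent variables: BDI-II, NSI, and SLS".

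Section 5.1 says that the study now runs remotely because of COVID-19. Section 5.5 marks, instrument by instrument, which measures are left out of telehealth visits, and Table 3 is the schedule updated for those visits.

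**The concern.** The name of the hypothesis and its outcome set describe different things. A cognitive test score records performance on a standard task; functional impairment concerns what a person can do in daily life. The protocol keeps these under separate headings.

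The difference matters for this treatment. CABA teaches compensation: planners, strategies and habits applied to real situations. Daily function could improve with no change in digit span or word fluency, or the reverse. In the sponsor's CABA pilot (Preliminary Studies), self-reported NSI and MSNQ scores improved significantly while no objective test reached significance. With five completers, one lacking a post-assessment, that is weak evidence, and those scales are not function measures. It does show that test scores need not move with what patients report.

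Followed as written, a gain on list learning or fluency would carry the label of reduced functional impairment, and a null result would say nothing about function.

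**Working it through.** **1. Outcome set against the protocol's own headings (Section 5.5)**

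| Instrument | Heading | Telehealth | Row in Table 3 |
|---|---|---|---|
| HVLT-R (1b) | Cognitive Functioning | not excluded | via NP Battery |
| Digit Span (1b) | Cognitive Functioning | not excluded | via NP Battery |
| COWAT (1b) | Cognitive Functioning | not excluded | via NP Battery |
| DKEFS Trails (1b) | Cognitive Functioning | excluded | no |
| Neuro-QOL | Cognitive Related Functional Impairment | excluded | no |
| Sheehan Disability Scale | General Functioning | excluded | no |
| CHART-SF | Social Role Participation | excluded | no |
| GOS-E | Global Outcome | excluded | no |

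Table 3 does not itemise the NP Battery; its contents are inferred from the Cognitive Functioning list. That Trails is not collected remotely rests on the explicit sentence in Section 5.5.

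- 1b variables filed under cognitive functioning: 4 of 4.
- Function, participation or global measures given by telehealth: 0 of 4.
- Instruments marked in Table 3 after week 0: CAPS-V, PCL-5, NSI, BDI-II, SLS, CSQ and NP Battery, 7 in all; filed under a function heading: 0. The NSI is filed as symptom severity and the SLS as quality of life.
- FOSQ-10 carries no telehealth exclusion, but it is described as a sleep measure and has no row in Table 3.

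**2. Time points.** Table 3 marks the NP Battery at weeks 0 and 14: 2 of the 3 levels in the 1b model.

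**3. What two time points do to the stated power.** The Sample size and power paragraphs claim at least 80% for a difference growing linearly to 0.5 SD, with 96 per group, 15% drop-out, autoregressive correlation 0.45 and an overall alpha of .01 to .02. Sidedness is not stated; two-sided is assumed here.

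The stated N is reproduced by an endpoint comparison at alpha .02:

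n = 2(2.326 + 0.842)² / 0.5² = 80.3, so 81 per arm; 81/0.85 = 95.3, so 96 per arm and 192 in total.

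For 1b at weeks 0 and 14, take n = 96 × 0.85 = 81.6 per arm, SD 1, two-sided alpha .03 (read as applying to 1b alone), critical value 2.170, and power = Φ(0.5/SE − 2.170). The correlation between weeks 0 and 14 is either 0.45² = 0.2025 (two autoregressive steps) or 0.45 (assumed upper value).

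Change contrast, SE = √[4(1 − ρ)/n]:
- ρ = 0.2025: SE = 0.1977; 0.5/SE = 2.529; power = Φ(0.359) = 64%.
- ρ = 0.45: SE = 0.1642; 0.5/SE = 3.045; power = Φ(0.875) = 81%.

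Baseline-adjusted week 14, SE = √[2(1 − ρ²)/n]:
- ρ = 0.2025: SE = 0.1533; 0.5/SE = 3.261; power = Φ(1.091) = 86%.
- ρ = 0.45: SE = 0.1398; 0.5/SE = 3.576; power = Φ(1.406) = 92%.

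These are for one variable, before any adjustment within the 1b set. At its strictest (Bonferroni, one score per test), that adjustment is .03/4 = .0075 with Trails and .03/3 = .0100 without it. Westfall-Young lies between these values and .03.

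**The case against.** The strongest reply is that Section 5.6 expressly attaches the label of functional impairment to these four tests. The analysis is therefore prespecified, and only its name is in question. It is true that no 1b variable is left undefined. But nowhere do the documents argue that the tests stand in for function. They give functional impairment its own heading and instrument, and they list cognitive function as a separate aim. The reporting wording is not given; the risk comes from the label.

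A reader might infer more than the documents support:

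- *That the trial holds no functional or Trails data at all.* Sections 5.1 and 5.5 tie the remote plan to the pandemic, and both instruments remain in the full battery. In-person data may exist; the number is not stated and could be anywhere from 0 to 192.
- *That the 1b model cannot be run.* A mixed model can be fitted to two scheduled time points, and Section 5.6 allows for missing assessments. The three time levels need a wording correction.
- *That the plan contradicts itself by calling neuropsychological performance exploratory.* The exploratory paragraphs can be read as covering tests not listed under 1b. A clarification is enough.
- *That 1b is underpowered.* That depends on the model and on an assumed correlation; a baseline-adjusted analysis exceeds 80% before adjustment within the set.

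**Conclusion.** The construct mismatch stands and nothing in the documents cures it. One of two primary hypotheses is named for functional impairment and tested only with cognitive tests (4 of 4). For remotely assessed participants, 1b cannot answer Aim 2 or goal 2 of the Abstract, because none of the four function or global measures is given. For in-person participants the 1b analysis still lists no functional measure. This needs correcting before analysis.

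Trails and the time levels are secondary consistency points. How much Trails data is lost cannot be sized, because the split between in-person and remote assessments is not given. The power figures rest on two-sided testing, .03 for 1b alone, equal variances, 15% loss and the assumed correlations. They are a reason to name the model, and the mismatch does not depend on them.

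**What to change.** Make one dated amendment before any cognitive data by arm are seen, and state in it whether any have been. Section 5.6 provides for interim analyses; its six-monthly safety data set names CAPS scores and serious adverse events.

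1. **Label.** In Section 5.6, the primary hypotheses, Aim 2 and goal 2 of the Abstract, rename 1b as objective cognitive performance. Add that 1b does not by itself support a conclusion about functional impairment. Distinguish it from the cognitive terms in goal 3 and Aim 3. If the NSI is named there, say whether the total or the cognitive items 13-17 are meant.
2. **Time, model and power.** State weeks 0 and 14, name the model (for example baseline-adjusted week 14), and restate the power for 1b on that basis, including adjustment within the set.
3. **Outcome set.** Fix the Westfall-Young set for 1b in advance. Say whether Trails stays, using the available in-person data, or becomes supportive. Say how in-person and remote scores are combined, including for participants who changed mode between baseline and week 14. Removing Trails loosens the strictest bound from .0075 to .0100, so this must not be decided after seeing results.
4. **Function.** Report any in-person Neuro-QOL data as the supportive functional outcome. Optionally add Neuro-QOL for the remaining assessments, if it can be given remotely with the mailed response key (Section 5.5), and state that it is incomplete.
5. **Consistency.** Align the opening sentence of *Importance of Knowledge to Be Gained*, which states without condition that the study evaluates effectiveness for functional impairment. Edits to *Relevance of the proposed work* and to the exploratory paragraphs are clarifications only.

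The cost is an amendment to a primary hypothesis, with IRB approval and site notification, and a narrower primary claim. No collected data are lost. The Neuro-QOL option adds participant time.
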